6 STATISTICAL CONSIDERATIONS

6.1 Primary Endpoint

Aim1: Identification of barriers and facilitators to HIV/STI prevention behavior to be addressed in the intervention and determine preferences for intervention format and delivery strategy.

Aim 2:

- Acceptability of PrEP in primary care will be measured with the Acceptability of the Intervention Measure (AIM).
- Feasibility, the extent to which the intervention could be successfully implemented within the setting, will be measured by the Feasibility of Intervention Measure (FIM).
- Appropriateness, the perceived fit of the intervention and relevance for the practice setting, will be measured with the Intervention Appropriateness Measure (IAM)

Aim 3: Prevention self-efficacy, an intermediate behavioral target in our theoretical model. This construct will be measured at baseline, intermediate, and final follow up visit using a

modified Generalized Self-Efficacy Scale (GSES) assessing HIV and STI prevention self-efficacy.

6.2 Secondary Endpoints

Aim 1: None

Aim 2: None

Aim 3:

- Referral feasibility: # potential participants referred/# eligible.
- Recruitment feasibility: # enrolled/# patients referred.
- Retention feasibility: # completing all sessions/# enrolled.
- Acceptability: Assessed at the final visit by a Coaching Satisfaction Survey
- Secondary outcomes:
 - a) Repeat STI test results at three-months and six-months.
 - b) Prevention behavior, including uptake of PrEP, condom use, HIV testing, and partner notification of positive STI results

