Aim 3: We will conduct 1) an iterative pilot phase followed by 2) a small RCT assessing intervention effect on the intermediate target of prevention self-efficacy. Pilot testing will occur over a 3-month period to prime intervention for implementation, with the aim of recruiting n=10 pilot participants. Pilot phase participants will follow the same study procedure timeline as participants randomized to the coaching intervention arm of the RCT, excluding the 6-month follow-up visit. Pilot participants will not be followed in the RCT or contribute outcome data. At the end of every health coaching visit (the baseline, 1-week, 1-month and 3-month visits), pilot phase participants will complete a brief feedback interview to ensure face validity and identify areas needing refinement. Feedback will be incorporated into the study design, with amendments submitted to the IRB as needed. The RCT will randomize youth with recent STI 1:1 to the coaching intervention vs a standard of care (SOC) control. If difficulty retaining coaching participants during the RCT generates a disparity in evaluable participants per arm, the RCT's randomization scheme will be changed to 2:1, intervention vs SOC, to balance numbers of evaluable participants per arm. Both arms (intervention and SOC) will have data collection visits at the baseline, the 3-month, and the 6-month-follow-up time points. In addition, the intervention group will have health coaching sessions at baseline, 1 week, 1 month and 3 months. At the end of the 3-month health coaching visit, a sample of RCT phase participants assigned to the intervention arm will complete a brief feedback interview to ensure face validity and identify areas needing refinement for future studies.

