3.1.3 Follow-up Phase

Aim 1: No intervention

Aim 2: No intervention

Aim 3: All RCT participants will have a 6-month follow-up visit. Participants in the intervention arm will be able to attend the follow-up visit if they attend at least one of the health coaching visits. For both arms, the follow up visit will consist of the same data collection (CASI and chart abstraction) as the 3-month visit.

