4.2 Study Intervention Phase

Aim 1: No intervention

Aim 2: No intervention

Aim 3: The discussion of the intervention phase is strictly for Aim 3 of the study project.

For the Aim 3 RCT phase, the participants randomized to the standard of care group will not undergo the health coaching intervention. The participants randomized to the health coaching group will attend health coaching sessions at the baseline, 1-week, 1-month and 3-month visits.

4.2.1 Follow up Visit 1

Aim 1: N/A

Aim 2: N/A

Aim 3: Both the health coaching group and the standard of care group will complete follow-up surveys at the 6-month follow-up visit.

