4.4 Subject Completion/Withdrawal

Aims 1, 2, 3: Participant completion of the study will be closely monitored in both treatment arms. Our criteria for defining study completion, withdrawal, drop out, and attrition is defined below.

Multiple attempts will be made to retain participants in the study. Participants in either treatment group who do not attend a visit after 3 unsuccessful contact attempts will be considered a no-show for that visit.

Subjects may withdraw from the study at any time without prejudice to their care. They may also be discontinued from the study at the discretion of the Investigator for lack of adherence to visit schedules. The Investigator may also withdraw subjects who violate the study plan, or to protect the subject for reasons of safety or for administrative reasons. It will be documented whether or not each subject completes the study. If the Investigator becomes aware of any serious, related adverse events after the subject completes or withdraws from the study, they will be recorded on the CRF.

Participants will be asked to provide at least three forms of secure contact information (e.g., cell phone, email, social media). In addition, participants will be asked about preferred method of contact, and will be asked for consent to text message. At the end of each study visit, participants will be scheduled for their next visit. We will use flexible visit windows for each coaching visit. Before the window opens, participants will be contacted via their preferred method to confirm their next appointment. If a participant does not respond after 2-3 attempts using one strategy (i.e., texting, emailing, calling) then a new outreach strategy will be used to diversify the approach. If a participant does not respond after five unanswered attempts, we will stop trying. Study staff will provide reminder contact (text, call or email) prior to each visit based on the participants preferred method. To facilitate follow up, the coaching sessions will not be restricted to the clinic, and instead coaches will

be able to meet youth in the community or over a CHOP-approved HIPAA compliant platform.

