For Aim 3, all participants will be patients of CHOP primary care clinics, and thus can be rapidly referred to clinicians and social workers in case there is a need to intervene for an identified mental health issue. Our mood rating instrument, the PSC-17, does not include any assessment of suicidal ideation. However, if a participant discloses suicidal ideation, homicidal ideation, or abuse during an intervention session, the PI will be notified immediately, as well as the clinic social worker. Based on clinician assessment, participants who report suicidal ideation will be referred to the local Emergency Department or psychiatric crisis center, as needed. Any reports of child abuse will be reported to the clinic social worker and reported to ChildLine in accordance with Pennsylvania State Law. All participants will be provided mental health resources at the end of the first session, irrespective of their score on the PSC-17.

Participants will complete a modified version of the Adverse Childhood Experiences survey. To minimize the risk to participants that may arise regarding fear of disclosing a specific form of adversity, the study will utilize a modified version of the ACES questionnaire that has been validated in middle and high school students. The modified inventory is presented in 7 items. Within each item, participants are presented with a diagram including 2-4 circles. Each circle contains the description of an ACE, with language adapted from the cited inventories. The wording has been modified to be appropriate for the reading and comprehension abilities of 14 to 18-year-olds. Participants are instructed to read the ACE description contained in each circle, to think back on their entire life, and to decide if the

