- Retention feasibility: Calculated as the proportion of participants who completed each follow-up coaching session over the total number of scheduled coaching visits. To determine if the mental health is associated with retention, I will use logistic regression to compare proportions of subjects retained between the following participant groups: high depressive symptoms, high trauma score, and substance abuse (see definitions in exploratory analysis section above), adjusting for demographic characteristics such as race and sex.

Fidelity will be assessed by reviewing baseline visit transcripts for the first ten participants and reviewing a random sample of 2 visits per week for ongoing supervision

- We will use the Motivational Interviewing Assessment-Supervisory Tools for Enhancing Proficiency (MIA-STEP) cut offs for fidelity: interventionist will have to demonstrate in the first ten sessions the use of at least half of the MI consistent items three to four times, namely, receive a “Somewhat” (4) frequency and extensiveness rating and at least an “Adequate” (4) skill level rating. In other words, the interventionist has to show capacity to use a moderate amount of MI strategies and skills and show an adequate level of performance when implementing them.
- On random sample, if three successive sessions occur in which they fall below proficiency standards, the interventionist will receive additional training, feedback, and coaching until he or she demonstrated again the minimal MI proficiency standards. Supervisors may elect to use the protocol’s MI proficiency standards as a supervisory benchmark for their clinicians. The MIA-Step MI rating worksheet tool (see below) will be used to assist in this task (<https://motivationalinterviewing.org/sites/default/files/mia-step.pdf>)
- In addition, the interventionist will complete the content checklist after each visit to assure each psychoeducation content domain (e.g. condoms, partner notification) was addressed in the session.
- Acceptability: I will calculate the proportion of participants who endorse each item on the Coaching Satisfaction Survey in the "agree" or "strongly agree" range.

Exploratory outcome analyses: Utilization of prevention behavior at the six-month time point. I will calculate the proportion of participants who:

- Initiate PrEP
- Do not develop repeat sexually transmitted infection (STI)
- Report 100% condom use
- Receive HIV testing
- Report partner notification of their initial STI

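### Sections 6.2 and 6.3.2 define Aim 3 retention and referral feasibility differently, and the 6.3.2 retention ratio divides people by visits

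*Combined protocol and SAP*

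**What the plan says.** The combined protocol and SAP defines the Aim 3 feasibility ratios twice.

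**Retention.** Section 6.2 lists "Retention feasibility: # completing all sessions/# enrolled". It does not say what a session is, or whether the denominator covers both arms. Section 6.3.2, under the secondary outcome analyses, describes the same endpoint this way: "Calculated as the proportion of participants who completed each follow-up coaching session over the total number of scheduled coaching visits". On mental health and retention, the same bullet adds: "I will use logistic regression to compare proportions of subjects retained between the following participant groups". It does not define retained.

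**Design facts that bear on this.** Section 3.1 states that "the intervention group will have health coaching sessions at baseline, 1 week, 1 month and 3 months". Section 4.2 states that "the participants randomized to the standard of care group will not undergo the health coaching intervention". Section 3.3.2 plans 150 RCT participants, 75 per arm, and sections 3.2 and 9.1.1 allow a later move to 2:1.

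**Referral.** Section 6.2 divides referred patients by eligible patients. Section 6.3.2 uses a different denominator, patients with a bacterial STI counted from the STI dataset, and gives no age limit. The Aim 3 inclusion criteria in section 3.4.1 cover ages 13 to 19. They accept treated, laboratory-confirmed trichomonas on the same footing as gonorrhea, chlamydia and syphilis.

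Recruitment feasibility, the third ratio, is the same in both sections.

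**The concern.** The two sections do not describe the same quantity for retention or for referral, and nothing elsewhere reconciles them. For retention, the section that is meant to give the calculation has people in the numerator and visits in the denominator, so full attendance does not give 100%. The regression in the same bullet needs an outcome, and the text does not say which definition provides it.

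Feasibility is named in Primary Aim 3 (section 2.1), and section 10 says the RCT findings will feed an application for a larger trial. The protocol also foresees difficulty in keeping coaching participants (sections 3.1 and 3.2). Retention is therefore a figure that readers will look for, and as written it depends on which section the analyst follows and how it is read.

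**Working it through.** The documents give no retention or referral rate, target or precision, so there is no figure of the plan's own to reproduce. The check is to put the planned counts into each definition.

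**Inputs.** 150 participants, 75 coached and 75 control (section 3.3.2). Four coaching sessions per coached participant, three of them after baseline (section 3.1 and Table 1). No coaching for controls during the trial (section 4.2); the single session offered to them after the study (section 7.1) falls outside it.

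**1. Section 6.3.2 read literally, full attendance.**
- Denominator of follow-up coaching visits: 75 / (75 × 3) = 75/225 = 33.3%.
- Denominator including the baseline coaching visit: 75 / (75 × 4) = 75/300 = 25%.
- If the ratio is formed separately for each session, the numerator is still 75 and the ceilings are the same.

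**2. Section 6.2, full attendance.**
- Coaching sessions, both arms in the denominator: (75 + 0)/150 = 50%. If 2:1 applied throughout, 100/150 = 66.7%.
- Coaching sessions, coaching arm only: 75/75 = 100%.
- Study visits, both arms: 150/150 = 100%.

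The 6.2 ratio can therefore be calculated. Its ceiling depends on a choice that the text leaves open.

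**3. How far the readings diverge on the same data.** Assume, for illustration, 80% attendance at each of the three follow-up sessions, with misses independent. The share of coached participants completing all three is 0.8³ = 51.2%, an expected 0.512 × 75 = 38.4 people.

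| Reading | Calculation | Result |
|---|---|---|
| Sessions completed / sessions planned | 180/225 | 80% |
| Completers of all three / coaching arm | 38.4/75 | 51.2% |
| Completers of all three / both arms | 38.4/150 | 25.6% |
| 6.3.2 literal, completers / follow-up visits | 38.4/225 | 17.1% |

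The first two rows are both sensible, and they need not agree. With 180 of 225 sessions attended there are 45 misses. If 45 people miss one each, completers are (75 − 45)/75 = 40%. If 15 people miss all three, completers are (75 − 15)/75 = 80%. The 80% attendance is an assumption; the spread shows only that the choice of definition matters.

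**4. Referral.** Let *t* be the trichomonas-only share of patients with any of the four infections, and *e* the share failing other criteria, taken as equal in both groups. With the same number referred, the 6.3.2 figure divided by the 6.2 figure is (1 − *e*)/(1 − *t*). Omitting trichomonas-only patients pushes the 6.3.2 figure up, and counting patients who fail age or other criteria pushes it down. The two cancel when *e* = *t*. The documents give neither share. Assumed values show that either direction is possible: *t* = 0.20 and *e* = 0 give 1.25, while *t* = 0.05 and *e* = 0.30 give 0.74.

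**The case against.** The best defence is that this is loose drafting that a sensible analyst would repair. Section 6.3.2 probably meant either sessions attended over sessions planned, or participants completing every follow-up session. Nobody would report 33% for full attendance. Because 6.3.2 confines retention to coaching, the coaching arm is the natural denominator for 6.2 as well, and the 50% ceiling then disappears. For referral, the STI dataset is a reasonable, countable stand-in for the eligible population, and it is already a recruitment source (section 3.1.1).

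Much of this is fair. But the two plausible intentions for 6.3.2 give different figures, neither is what is written, and the choice would be made with the data in hand. The word bacterial would lead an analyst to run a query that leaves out a qualifying infection.

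A reader might infer three stronger points that the documents do not support.

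- *Neither retention formula works.* Only 6.3.2 has a units fault. Section 6.2 is people over people and works once the arm and the sessions are fixed. Section 5.3 does say "All participants will be provided mental health resources at the end of the first session", which loosens the word session, but most Aim 3 text uses it for coaching.
- *The regression has no possible outcome.* It could borrow the 6.2 numerator, or model sessions attended out of sessions planned. The fault is that the plan does not say which.
- *The denominator shrinks after a missed visit*, because section 4.4 says "At the end of each study visit, participants will be scheduled for their next visit". That sentence concerns booking. Scheduled coaching visits reads naturally as the visits fixed in Table 1, and nothing says a missed visit removes the later ones.

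**Conclusion.** The point holds. Retention and referral feasibility are each defined in two conflicting ways. The 6.3.2 retention ratio has a units error that caps it at 33% (25% if baseline visits are counted). The 6.2 ratio is capped at 50% at 1:1 only if sessions means coaching sessions and enrolled means both arms. The retention regression does not name its outcome definition. These ceilings rest only on the planned counts; the comparison at 80% attendance is illustrative.

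For referral, the fault is the mismatch with the eligibility criteria. No size or direction of error should be claimed, because the shares needed are not in the documents.

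A reader might also infer that the plan must report study-visit retention by arm, since section 3.1.3 says "Participants in the intervention arm will be able to attend the follow-up visit if they attend at least one of the health coaching visits". That would be an additional measure. Neither section proposes it as a feasibility endpoint, so its absence is not an error.

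The impact is modest. These are secondary descriptive endpoints with no Aim 3 threshold, and the primary analysis and sample size are unaffected.

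**What to change.** Use one definition of each ratio in both sections.

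(a) **Retention:** participants randomised to coaching who complete all follow-up coaching sessions (1 week, 1 month, 3 months), divided by participants randomised to coaching. Name this as the yes/no outcome of the retention regression. Report sessions completed over sessions planned, three per coached participant, alongside it. Neither ceiling then depends on the allocation ratio, so a move to 2:1 does not change the meaning.

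(b) **Referral:** referred patients, divided by patients aged 13-19 at the recruiting clinics with laboratory-confirmed gonorrhea, chlamydia, trichomonas or syphilis in the study period, from the STI dataset. State which eligibility criteria could not be applied from that source, for example language or device access.

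Report the raw counts for both.

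The cost is wording and tabulation. Retention needs no new data. For referral, section 5.1.1.3 (Aim 1) already lists trichomonas among the diagnoses drawn from the medical record and the team's database, so a wider query should be enough.

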6.3 Statistical Methods

6.3.1 Baseline Data

Aim 1: Study information will be gathered through focus group and in-depth interview data. Themes from the focus groups and in-depth interviews will be reported and will be used to inform aims 2 and 3. Data from the baseline CASI summarized by standard descriptive summaries (e.g. means and standard deviations for continuous variables such as age and percentages for categorical variables such as gender). These data will be used to help identify whether different themes emerge from different populations of youth by sex, gender, and sexual orientation.

Aim 2: Baseline and demographic characteristics will be summarized by standard descriptive summaries (e.g. means and standard deviations for continuous variables such as age and percentages for categorical variables such as gender). Themes from the individual interviews and results from the chart simulated recall will be reported and be used to inform aim 3.

Aim 3: Baseline and demographic characteristics will be summarized by standard descriptive summaries (e.g. means and standard deviations for continuous variables such as age and percentages for categorical variables such as gender). We will also report baseline data from the multiple scale instruments, such as sexual behavior, substance use, risk perception and stigma scales, etc. (See section 5.1.3.1 for list of instruments.)

6.3.2 Analysis

Aim 1: We will conduct a deductive qualitative analysis of focus group transcripts and in-depth interview transcripts with our theoretical model guiding the coding process. Codes related to model constructs will be assigned to interview segments to organize the data, using the software NVivo, with two study team members separately reviewing the first 10 transcripts line by line, assigning codes as concepts become apparent. We will compare text segments to those that have been previously assigned the same code, and to segments coded separately by each analyst, to decide whether they reflect the same concept. We will use this process to generate a coding scheme, then apply it to all transcripts. Once coding is complete, we will review the data to document emerging themes-general insights gleaned from the entirety of the data- which may inform intervention content.

Aim 2: Survey data will be summarized via descriptive statistics. We will set a >80% threshold for high acceptability, feasibility and appropriateness. The interview coding process will parallel that described in Aim 1. We will use an integrated deductive and inductive coding approach. Transcripts will be reviewed using deductive methodology, where CFIR determinants will be used as the coding framework. After completion, the transcripts will be re-reviewed using inductive methodology where codes identifying novel barriers and facilitators of implementation that do not map onto the CFIR will be identified and used to develop a coding framework that is then applied to all transcripts. We will integrate the qualitative and quantitative data by merging findings through a comparative coding analysis. The AIM and FIM scores will be dichotomized (completely disagree/disagree vs completely agree/agree). We will compare the distribution of content themes between providers with high vs low acceptability and, separately, high vs low feasibility ratings. Data will then be used as a starting point in which to build an optimized PrEP-inclusive coaching implementation strategy to be tested in the subsequent RCT.

Aim 3: The primary analysis will be based on an intention to treat approach and will include all subjects randomized at Visit 1.

The primary outcome for the RCT is the change in prevention self-efficacy between intervention and control conditions between the baseline and six-month (final) visits. We will compare the exposure variable of treatment group with the outcome variable of continuous score on the modified Generalized Self-Efficacy Scale at baseline, intermediate (e.g. three month), and six-month visits using mixed effects logistic regression models with a random intercept for patient and a random slope for time. In exploratory analyses, to determine if the mental health predictors impact the self-efficacy outcome, we will create separate mixed effects regression models to compare self-efficacy score for those with and without mood ratings consistent with depression on the PSC-17, high trauma (Adverse Childhood Experiences Scale score >4 vs not), and substance abuse (CRAFFT score >4) adjusting for treatment group and demographic characteristics including sex. In order to assess the impact of STI timing on the primary outcome of prevention self-efficacy, we will use linear regression models and days between STI diagnosis and the first coaching visit in the intervention group, adjusting for demographic covariates including sex and sexual orientation. Finally, we will assess if coaching may have a significant effect on other domains in the self-efficacy pathway of our model, by repeating the primary analysis above with scores for the Patient Activation Measure [PAM], and Confidence in Safer Sex Scale.

There will be no adjustment of p value for multiple comparisons given the exploratory nature of these analyses.

Secondary outcome analyses:

- Referral feasibility: Calculated as the number of potential participants referred to study staff over the number of patients with bacterial STI at the clinics during the study period. This denominator will be identified using the CHOP STI dataset.
- Recruitment feasibility: Calculated as the number of patients enrolled over the number of patients referred.
- Retention feasibility: Calculated as the proportion of participants who completed each follow-up coaching session over the total number of scheduled coaching visits. To determine if the mental health is associated with retention, I will use logistic regression to compare proportions of subjects retained between the following participant groups: high depressive symptoms, high trauma score, and substance abuse (see definitions in exploratory analysis section above), adjusting for demographic characteristics such as race and sex.

Fidelity will be assessed by reviewing baseline visit transcripts for the first ten participants and reviewing a random sample of 2 visits per week for ongoing supervision

- We will use the Motivational Interviewing Assessment-Supervisory Tools for Enhancing Proficiency (MIA-STEP) cut offs for fidelity: interventionist will have to demonstrate in the first ten sessions the use of at least half of the MI consistent items three to four times, namely, receive a “Somewhat” (4) frequency and extensiveness rating and at least an “Adequate” (4) skill level rating. In other words, the interventionist has to show capacity to use a moderate amount of MI strategies and skills and show an adequate level of performance when implementing them.
- On random sample, if three successive sessions occur in which they fall below proficiency standards, the interventionist will receive additional training, feedback, and coaching until he or she demonstrated again the minimal MI proficiency standards. Supervisors may elect to use the protocol’s MI proficiency standards as a supervisory benchmark for their clinicians. The MIA-Step MI rating worksheet tool (see below) will be used to assist in this task (<https://motivationalinterviewing.org/sites/default/files/mia-step.pdf>)
- In addition, the interventionist will complete the content checklist after each visit to assure each psychoeducation content domain (e.g. condoms, partner notification) was addressed in the session.
- Acceptability: I will calculate the proportion of participants who endorse each item on the Coaching Satisfaction Survey in the "agree" or "strongly agree" range.

Exploratory outcome analyses: Utilization of prevention behavior at the six-month time point. I will calculate the proportion of participants who:

- Initiate PrEP
- Do not develop repeat sexually transmitted infection (STI)
- Report 100% condom use
- Receive HIV testing
- Report partner notification of their initial STI

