3.2 Allocation to Treatment Groups and Blinding

Aim 1: N/A

Aim 2: N/A

Aim 3: Non-stratified 1:1 randomization will occur at baseline using the REDCap randomization tool based on randomization tables. The study team will not be able to change study groups for participants once randomization has taken place. The randomization will not be blinded to the participants or the study team because of the nature of the intervention.

As mentioned in Section 3, if difficulty retaining coaching participants during the RCT generates a disparity in evaluable participants per arm, the RCT's randomization scheme will be changed to 2:1, intervention vs SOC, to balance numbers of evaluable participants per arm.

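### The plan makes a contingency for poorer retention in coaching, but its only intention-to-treat analysis relies on missing at random, so the effect of assignment can be overstated

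*Combined protocol and SAP*

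**What the plan says.** All references are to the combined protocol and SAP, Aim 3.

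- **Population.** Section 6.3.2: "The primary analysis will be based on an intention to treat approach and will include all subjects randomized at Visit 1". Section 9.1.1 places the baseline survey before randomisation, so every randomised participant should have at least a baseline score.
- **Model.** Section 6.3.2 specifies the primary comparison "using mixed effects logistic regression models with a random intercept for patient and a random slope for time". The outcome is the modified GSES score, taken at entry, 3 months and 6 months. The score is continuous, so the logistic label does not fit. That is a separate matter, and the linear form is used below.
- **Retention.** Section 3.1, repeated in substance in 3.2 and 9.1.1, provides for the case where "difficulty retaining coaching participants during the RCT generates a disparity in evaluable participants per arm". The allocation is then "changed to 2:1, intervention vs SOC, to balance numbers of evaluable participants per arm". The word evaluable is not defined.
- **Six-month visit.** Section 3.1.3: "Participants in the intervention arm will be able to attend the follow-up visit if they attend at least one of the health coaching visits". SOC has no matching condition.
- **Missing scores.** Section 4.4.1 deals with interrupted, partial or redacted surveys. No section states how a missing 3-month or 6-month GSES is handled, which assumption applies, or any sensitivity analysis. Section 6.4 allows for up to 10% loss, not split by arm.

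**The concern.** A likelihood-based mixed model can include everyone randomised because it fills the gaps by assumption. Given the scores already observed, a coaching participant with no six-month score is taken to follow the coaching participants who have one. If those who disappear gained less, the estimate moves from the effect of being assigned to coaching towards the effect in those who remained under observation.

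The plan treats unequal retention as a problem of numbers. A 2:1 allocation restores the counts, but it does not change who in the coaching arm is missing or how their scores are predicted.

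Section 3.1.3 adds a second route to the same problem. A participant randomised to coaching who attends no session is barred from the six-month visit, while an equally disengaged SOC participant is not. That cannot be squared with an analysis of all randomised subjects.

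Section 10 says the findings will support an application for a larger multi-site trial. An overstated effect would carry over into the size of that trial.

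**Working it through.** **The plan's own figure.** Section 6.4 gives a detectable difference of 0.7 to 0.9 SD with 75 per arm, 80% power, two-sided alpha 0.05 and correlation 0.01 to 0.3, but no formula. A plain change-score calculation, (1.96 + 0.84) × √(2(1 − ρ)) × √(2/n), gives 0.64 to 0.54 with n = 75, and 0.68 to 0.57 with n = 67.5 (10% loss). A variant with SD √(2(1 + 2ρ)) and n = 67.5 gives 0.69 to 0.86, close to the stated range. The figure is not treated as wrong here. Only its lower end, 0.7, is borrowed, and the ratios below do not depend on it.

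**Inputs.** From the plan: visits at baseline, 3 and 6 months; 10% loss, applied here to SOC. Assumed, because the documents give no values:
- D = 0.7 SD, the six-month benefit in coaching participants who stay
- L, the share of the coaching arm who leave
- k, the share of D that leavers keep
- f, the share of leavers who still answer the surveys

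**Formulas**, for leavers who otherwise have a baseline score only:
- Effect of assignment = D × [(1 − L) + kL]
- Model estimate = D × [(1 − L) + kfL] / [(1 − L) + fL]

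SOC loss does not enter, because SOC leavers are assumed to behave like other SOC participants.

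**Upper bound (k = 0, f = 0).** The model returns 0.70 throughout.

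| Coaching loss L | Effect of assignment | Overstatement |
|---|---|---|
| 10% | 0.7 × 0.9 = 0.63 | 11% |
| 20% | 0.7 × 0.8 = 0.56 | 25% |
| 30% | 0.7 × 0.7 = 0.49 | 43% |
| 40% | 0.7 × 0.6 = 0.42 | 67% |

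**Other cases at L = 30%.**

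| Leavers | Model | Effect of assignment | Overstatement |
|---|---|---|---|
| keep half, none answer | 0.70 | 0.49 + 0.105 = 0.595 | 18% |
| keep none, half answer | 0.49/0.85 = 0.576 | 0.49 | 18% |
| keep half, half answer | 0.5425/0.85 = 0.638 | 0.595 | 7% |
| all answer | 0.49 (k = 0) | 0.49 | none |
| keep all | 0.70 | 0.70 | none |

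In the second row, rounding to 0.57 and 0.49 before dividing would give 16%. At L = 10% with half the benefit kept and no answers, the result is 0.70/0.665, or 5%.

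**Simulation check.** A Gaussian repeated-measures model was fitted by maximum likelihood with unstructured covariance, 100,000 per arm and correlation 0.01 to 0.6. With leavers lost before the 3-month survey and keeping no benefit, it gave 0.70 to 0.71 at every loss rate tried (10%, 30%, 50%). With leavers lost after the 3-month survey, at 30% loss, it gave 0.65 to 0.69 against about 0.48 to 0.50. An observed 3-month score therefore corrects only a small part of the bias. With half the leavers answering it gave 0.573 against 0.487. With all answering, the two agreed.

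**The 2:1 switch.** The allocation ratio appears in neither formula. Evaluable numbers are equal under 2:1 only if coaching retention is half of SOC retention, for example 45% against 90%. The upper-bound ratio is then 1/0.45, about 2.2.

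**What a sensitivity analysis adds.** At 30% loss with half the benefit kept and no answers, the mixed model gives 0.70, and giving leavers the SOC mean gives 0.7 × 0.7 = 0.49. The truth, 0.595, lies between them.

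**The case against.** The strongest reply is that stopping coaching is not the same as a missing score. Anyone who attended one session may attend month 6, and the first session belongs to the baseline visit (Table 1, section 4.1). Both arms are surveyed at 3 and 6 months and paid $40 for each of those visits (section 9.7). A missed visit counts as a no-show for that visit only, and discontinuation for poor attendance is discretionary (section 4.4). A participant who quits coaching but answers at month 6 is analysed as observed. This stands. A reader might infer that the planned analysis simply estimates the effect of completing coaching, but the documents do not support that: the bias arises only where scores are missing.

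Second, a reader might infer that the plan expects drop-out concentrated in coaching. The text is conditional, and the only loss figure is 10% overall. It is a contingency, and the point is worded accordingly.

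Third, no retained benefit is an extreme assumption, since section 7.1 describes an intensive first session with education, counselling, a personal plan and referral. This also stands, so 11% to 67% is an upper bound and not a forecast. If leavers did better than the model predicts, the bias would run the other way.

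Fourth, reference-based imputation might be called mere preference, because it can err downwards as far as the mixed model errs upwards (0.49 and 0.70 around 0.595). That does not defeat it. Bracketing the answer is the purpose of a sensitivity analysis.

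**Conclusion.** The point holds in conditional form. The plan foresees the possibility of coaching-specific loss, answers it only with allocation, and states neither a missing-data assumption nor a sensitivity analysis for its single intention-to-treat model. The overstatement needs two things together: missing six-month scores in coaching, and leavers who do worse than the model predicts. Loss rates by arm and the benefit kept by leavers are assumptions, because the documents give neither.

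At 30% coaching loss the plausible range runs from none to 43%. For a later trial planned on 0.70 SD, the worst case at that loss would call for (0.70/0.49)² ≈ 2.0 times the planned size, and the half-benefit case for (0.70/0.595)² ≈ 1.4 times.

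Apart from any arithmetic, sections 3.1.3 and 6.3.2 contradict each other. The mixed model itself, in linear form, remains a reasonable primary analysis.

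**What to change.** 1. Keep the mixed model as primary, and state the estimand (effect of assignment) and the missing-at-random assumption.
2. Reconcile section 3.1.3 with section 6.3.2 so that 3-month and 6-month surveys are sought from everyone randomised, whatever their coaching attendance. This helps most, because the bias vanishes if all leavers answer.
3. Pre-specify one reference-based multiple imputation analysis for coaching participants without a six-month GSES, and name the variant correctly. Jump to reference moves the participant to the SOC mean after drop-out. Imputing from the SOC distribution given the observed 3-month score is copy reference.
4. Report it beside the primary estimate, with six-month completeness by arm.
5. State in advance when the result will be called robust, for example same direction and a confidence interval still excluding zero.

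The cost is one extra analysis and some follow-up effort for participants who have stopped coaching. The sensitivity estimate will usually be smaller than the primary one.
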